6.3. Statistical Methods

Our analytical plan was developed with [name], the biostatistician for the CEMALB who will oversee all statistical analysis. In all analyses, criterion for significance will be $p \leq 0.05$. All statistical estimates will be tabulated along with the corresponding confidence intervals.

Our primary endpoint is identification of subjects who achieve a $\geq 15\%$ fall in FEV₁ during hours 3-10 following allergen challenge. We will subtract the pre-allergen challenge %FEV₁ value from the post-allergen %FEV₁ value to make this determination.

For analysis of secondary endpoints, we will first use linear regression to determine if there is a linear relationship between baseline sputum IL-1 β concentration (pg/mL) and asthma outcomes (maximum fall in %FEV1 during LPR, methacholine reactivity defined by the dose required to produce a $\geq 20\%$ drop in FEV1, sputum granulocyte content both in terms of % of total cell count and cells/mg of sputum, exhaled nitric oxide concentration) following allergen challenge, adjusting for potential confounders. The point estimate and confidence interval will be reported for the effect of baseline sputum IL-1 β on asthma outcomes. If the normality assumption is violated or there exists a non-linear relationship, we will calculate the Spearman correlation coefficient between baseline sputum IL-1 β concentration and asthma outcomes.

For analysis of exploratory endpoints, we will use two sample comparison tests to compare systemic inflammatory markers and gene expression levels before and after allergen challenge. We will use two-sample t tests or Mann Whitney U tests depending on whether the normality assumption is met. The point estimate and confidence interval will be reported for mean changes. We will transform the data to achieve normality if needed. HRV endpoints are exploratory, as we do not know if there will be changes during bronchospasm.

As we have considered additional individuals in our sample size calculation, we do not anticipate missing data will be a major issue affecting our study power.

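### The Spearman fallback for the secondary endpoints does not carry over the confounder adjustment that section 6.3 sets for the regression

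*Combined protocol and SAP*

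**What the plan says.** Section 6.3 (Statistical Methods) opens the secondary analysis with "For analysis of secondary endpoints, we will first use linear regression to determine if there is a linear relationship between baseline sputum" IL-1β and each post-challenge outcome: the maximum late-phase (LPR) fall in %FEV1, methacholine reactivity, sputum granulocytes and exhaled nitric oxide. The model is fitted "following allergen challenge, adjusting for potential confounders", and a point estimate with confidence interval is promised for the IL-1β effect. No confounder is named.

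The fallback has two triggers and one response: "If the normality assumption is violated or there exists a non-linear relationship, we will calculate the Spearman correlation coefficient between baseline sputum IL-1"β and the outcomes. No covariate, partial correlation or rank regression is mentioned, and neither is a diagnostic or threshold for the triggers. The synopsis (Statistical And Analytic Plan) has the same rule.

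Section 6.3 does contain "We will transform the data to achieve normality if needed", but in the paragraph on exploratory endpoints. It is not offered as a step before Spearman for the secondary endpoints.

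**The concern.** The two steps test different hypotheses. The regression asks whether IL-1β is associated with the outcome given the confounders. A two-variable Spearman coefficient asks whether there is any crude monotone association. Non-normal residuals are a reason to change the scale or the standard error, but not a reason to stop adjusting.

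Three things are at stake:

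- An outcome that switches can show a significant IL-1β association produced only by a shared confounder, or can lose a real adjusted association when the confounding runs the other way.
- The set of secondary results may mix adjusted and crude p-values, with the mix decided by the data.
- If the fallback replaces the regression, the adjusted effect in outcome units is lost for those outcomes.

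Separately, non-linearity is one of the triggers, yet Spearman responds only to the monotone part of a relation.

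**Working it through.** **Inputs from the documents.** The significance criterion is 0.05 (6.3); two-sided is assumed. No sample size or power is stated for the IL-1β analysis, so there is no figure of the plan's own to reproduce; the calculation in 6.4 concerns the anakinra trials. Screening stops at 25 LPR subjects, with at most 100 screened (6.4). If about 50–56% of those challenged have an LPR (1.3 and the cat-extract study in 1.4), 25/0.56 ≈ 45 to 25/0.50 = 50 subjects are challenged. At the conservative yield in 6.4, 25/(0.5 × 0.5) = 100. N=50 is therefore the main case.

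**Outcome spread.** The only spread given for the LPR fall is 25.6% ± 9.8% (6.4, from a cited challenge model). The coefficient of variation is 9.8/25.6 = 0.38, which for a lognormal means a log SD of √ln(1 + 0.38²) ≈ 0.37. A more skewed outcome, such as a cell count might be, is represented by log SD 0.8. That value is an assumption.

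**Assumed model.** One confounder C has correlation r with log IL-1β (log SD 1) and r with log outcome, and IL-1β has no effect given C. The crude log-scale correlation is then r × r: 0.09 at r=0.3 and 0.25 at r=0.5. The plan's sequence is simulated as raw-scale adjusted regression, Shapiro-Wilk on its residuals (the plan names no test), then Spearman if that test rejects.

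**Rejection rate at 0.05 with no adjusted effect, N=50** (2,000–4,000 simulated data sets per setting, so good to about one percentage point):

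| r | Sequence, log SD 0.37 | Sequence, log SD 0.8 | Adjusted log regression or partial Spearman |
|---|---|---|---|
| 0.2 | about 6% | about 6% | about 5% |
| 0.3 | 9% | 8–9% | about 5% |
| 0.4 | 14% | 17–19% | about 5% |
| 0.5 | 27% | 36–38% | about 5% |

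The normality check triggers Spearman in about 55–65% of data sets at log SD 0.37 and about 95% or more at log SD 0.8. With a normal outcome it triggers in about 5%, and the sequence stays at 5–8%.

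**Other sample sizes.** At N=100 and log SD 0.8, the sequence gives 13–14%, 31–34% and 66–67% for r = 0.3, 0.4 and 0.5. At N=25, plain Spearman gives about 6.6% at r=0.3 and 20% at r=0.5.

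**Opposite direction.** Let C correlate 0.4 with log IL-1β and −0.4 with log outcome, and let the part of IL-1β independent of C have a true effect of 0.3 SD. The crude correlation is 0.4 × (−0.4) + 0.3 × √0.84 = −0.16 + 0.275 = 0.115. The partial correlation is 0.3/√0.84 = 0.327. Power at N=50 is about 12% for Spearman, 55% for partial Spearman and 64% for adjusted log regression. At N=100 it is about 18–19%, 86% and 91–92%.

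**Non-linearity trigger.** For a symmetric U-shape explaining 16% of the variance, Spearman detects about 7% at N=50 and N=100. A two-degree-of-freedom quadratic test detects about 69% and 94%.

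**The case against.** The strongest reply is that the stated objective (2.2 and 6.2) is whether baseline IL-1β is predictive. A marker linked to an outcome through a third variable does predict it marginally, and Spearman holds 5% for its own null. This stands. The rates above are errors only against the adjusted null, so the claim is limited to IL-1β looking *independently* predictive. It does not remove the point, because 6.3 chose adjustment and speaks of the effect of IL-1β.

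A reader might infer that the plan withdraws the adjusted regression once a check fails. The documents do not say so. The regression comes first, the promise of an estimate and interval is unconditional, and 6.3 also promises intervals for all estimates. Replacement is the natural reading but remains an inference. If both results are meant, the plan should say which one governs.

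A reader might also infer that the fallback is almost automatic and the inflation large for every outcome. That is not supported. No confounder, correlation or IL-1β distribution is given. At a spread like the one quoted for the LPR fall, the check fires in only some data sets, and the highest rates need strong confounding or N=100. Section 9.4 allows sputum induction and methacholine testing to be skipped for safety, so numbers may be lower still.

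Nor do the documents suggest a U-shape. The rationale in 1.1 is monotone: higher IL-1β, and positive correlations with granulocytes (r=0.83 and 0.89). A symmetric U is Spearman's worst case; an asymmetric curve would be partly detected, and an analyst who had just found curvature would know of it.

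Finally, this is a secondary analysis without a power claim. Neither the primary endpoint nor eligibility for the anakinra trials depends on it.

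**Conclusion.** The gap is real and should be closed. Section 6.3 and the synopsis adjust the regression and leave the fallback unadjusted, and nothing elsewhere in the documents carries the covariates, or a transformation, into that step. Under the assumed single-confounder lognormal model at about N=50, the chance of a significant IL-1β result with no adjusted effect rises from about 5% to 8–9% for moderate confounding (r=0.3) and to 27–38% for strong confounding (r=0.5). It is about 6% at r=0.2 and near nominal for near-normal outcomes. These figures show sensitivity and do not predict what this study will find. That a non-monotone curve would often be missed is a possibility, not an expectation.

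**What to change.** Replace the fallback sentence in section 6.3 and in the synopsis with:

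*If residuals are non-normal, IL-1β and/or the outcome will be log-transformed (or rank-transformed) and the same covariate-adjusted model refitted. Any rank correlation used for inference will be the partial Spearman correlation adjusting for the same covariates, with its confidence interval. If the relationship remains non-linear after transformation, a quadratic term for log IL-1β will be added and the linear and quadratic terms tested jointly.*

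An unadjusted Spearman coefficient may still be reported, labelled as descriptive. The covariates should be named so that both steps use the same set.

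The cost is wording in two places and a few lines of code, with no new data, visits or subjects. Effects on a log or rank scale are slightly harder to describe, and the quadratic term uses one degree of freedom, which matters a little if the usable sample is small.

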4. STUDY PROCEDURES

4.1. Screening/Baseline Visit Procedures:

Potential participants will be initially screened for eligibility through a separate screening protocol (IRB#98-0799).

Within 12 months of completing the screening protocol, they will return for Visit 1. Sensitization to cat as determined by skin testing or IgE levels is not expected to change over the course of 12 months. Participants will have to meet all eligibility criteria at the time of the Baseline Visit. On Visit 1:

1. Consent will be obtained
2. Review of subject's medical history and current medications. Allergy skin prick test results from screening protocol #98-0799 will be included in the history.
3. Vital sign measurements (temperature, pulse, respiratory rate, blood pressure), oxygen saturation, and symptom scoring
4. Urine pregnancy test for women of child bearing potential
5. eNO
6. Spirometry
7. Venipuncture for CBC with Diff, Total and cat hair IgE, cytokines, and gene expression (approximately 50 cc total)
8. Physical exam of the ears, nose, throat and chest
9. Sputum induction
10. Collect nasal epithelial lining fluid (ELF).

After completion of the baseline visit, and if for any reason that subject cannot return for the challenge session in the required time, a repeat baseline visit will be done. At this visit the subject will repeat the following:

1. review history and meds
2. vitals

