4.2. Intervention/Treatment procedures

Visit 2: Methacholine Challenge Day (at least 2 days but less than 2 weeks after the baseline visit V1)

1. Review any change in medical status since last visit
2. Vital signs, oxygen saturation, and symptom score
3. Urine pregnancy test
4. Baseline HRV measurement
5. eNO
6. Spirometry
7. Physical exam of the ears, nose, throat and chest

8. Methacholine challenge if inclusion and exclusion criteria are still met (refer to section 5.4 for methacholine challenge procedure)

Visit 3: Allergen challenge day (24-48 hours after V2)

1. Review any change in medical status since last visit
2. Vital signs, oxygen saturation, and symptom score
3. Placement of the HRV device
4. Placement of the ASSIST devices (cardiac electrodes and wrist band)
5. eNO
6. Collect nasal ELF
7. Spirometry
8. If inclusion and exclusion criteria are still met, allergen challenge will be performed as described in section 5.1.
 - a. If subject is asymptomatic and FEV1 drops $<10\%$ at the completion of allergen challenge, subjects will be monitored for 2 hours post challenge and will be discharged following post-challenge venipuncture with rescue medications (albuterol with aerochamber and oral prednisone 60 mg), instructions for use of these medications if asthma symptoms occur, and contact information for the on-call physician. Subject will resume protocol beginning with Study visit 4 detailed below.
 - b. Any subject whose FEV1 drops $\geq 10\%$ will stay for the 10 hour post-allergen monitoring period as outlined below.
9. Collect nasal ELF after completion of the allergen challenge, either following the dose producing a 20% or greater fall in FEV1 (in early phase responders) or following completion of the highest dose of inhaled allergen (in those who do not exhibit an early phase response).
10. Post-challenge monitoring of vital signs every 10 minutes for the 1st hour, then every 30 minutes until 2 hours post-challenge, then hourly until 10 hours post-challenge
11. Spirometry when vital signs are obtained
12. eNO hourly between 2 and 10 hours post-challenge
13. Collect nasal ELF at 7 hours post-challenge (7 hours after the onset of the early phase response).
14. Venipuncture for CBC with diff, cytokines, and gene expression 10 hours post-challenge (approximately 50 cc total)

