15. All subjects will receive 4 puffs of albuterol 10 hours post-challenge. Spirometry will be performed 15 minutes after albuterol if post-challenge FEV1 at 10 hours was not approximately within 10% of baseline.
 - a. Albuterol will be repeated every 20 minutes up to three doses if repeat FEV1 is not within approximately 10% of baseline value or if subject remains in distress.
 - b. If needed, after three inhaled albuterol treatments, additional medications, including nebulized albuterol, atrovent and oral prednisone 60mg, will be given per physician discretion.
16. Subjects will be discharged 10 hours following allergen challenge when clinically stable and when FEV1 is within approximately 10% of baseline FEV1. HRV monitoring will be discontinued prior to discharge. At discharge, all subjects will be provided with an albuterol inhaler and aerochamber, a single dose of oral prednisone 60 mg, clear instructions for use of rescue medications in the event of symptoms related to bronchoconstriction, and contact information for the on-call physician. Subjects will reside overnight at their home if their residence is within 10 miles of UNC or a local hotel within 10 miles of UNC.

Visit 4: 24 hours post challenge

1. Vital signs, oxygen saturation, and symptom score
2. eNO
3. Spirometry
4. Venipuncture for CBC with Diff, gene expression, cytokines (approximately 50 cc total).
5. Methacholine challenge.
6. Sputum induction.
7. Collect nasal ELF.

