6.2. Secondary Endpoint

In addition to identifying subjects for participation in the planned studies of Anakinra vs placebo for mitigating features of asthma exacerbation, the additional purpose of this study is to determine if IL-1 β concentrations in the sputum at baseline before challenge are predictive of key asthma outcomes following inhaled allergen challenge

- 1) Baseline sputum IL-1 β concentration (pg/mL)
- 2) Asthma outcomes following allergen challenge as measured by:
 - a). maximum drop in %FEV1 during LPR
 - b). Change in methacholine reactivity from baseline pre-allergen measurement to 24 hours after allergen challenge.
 - c). exhaled nitric oxide (eNO) level
 - d). induced sputum:
 - i. Granulocyte (neutrophils/eosinophils) numbers and percentages
 - ii. Mucins (secretion of MUC5AC and MUC5B determined by Western blot and ELISA)

Exploratory Endpoints

Additionally, as exploratory endpoints, we will assess the effects of allergen challenge on markers of systemic inflammation and changes in inflammatory gene expression as described below:

- a). **venipuncture** for assessment of systemic inflammatory markers (CBC with differential for absolute neutrophil count and absolute eosinophil count), pro-inflammatory cytokine levels such as IL-1 β , IL-6, IL-8).
- b). **nasal ELF** for assessment of inflammatory mediators associated with allergen-induced airway inflammation.
- c). **gene array analysis** from blood and induced sputum at the baseline visit, again on the day of the challenge and, finally, at 24 hours post challenge. To identify signaling pathways potentially impacted by allergen challenge, we will use Nanostring® technology to measure differential expression of a panel of 594 immunology-related genes. This will be accomplished by collecting and isolating peripheral blood mononuclear cells from venous blood samples collected before allergen challenge, during allergen challenge, and 24 hours after allergen challenge.
- d). **heart rate variability** measurement via commercially-available monitor (Space Labs, Inc). We will identify if specific cardiac changes occur during allergen-induced asthma exacerbation.

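### Before/after blood markers and gene expression from the same subjects are to be compared with independent-samples tests, which ignore the pairing

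*Combined protocol and SAP*

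**What the plan says.** Section 6.3 sets the rule for the exploratory endpoints, with the challenge as the dividing point: "For analysis of exploratory endpoints, we will use two sample comparison tests to compare systemic inflammatory markers and gene expression levels before and after". The next sentence names the tests: "We will use two-sample t tests or Mann Whitney U tests depending on whether the normality assumption is met". The one after it promises an estimate: "The point estimate and confidence interval will be reported for mean changes".

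The samples come from one group measured repeatedly. Sections 3.1 and 8 describe a single-arm, open-label study. For gene expression, section 6.2 lists "venous blood samples collected before allergen challenge, during allergen challenge, and 24 hours after allergen challenge". The visit schedule matches:

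- Visit 1 (section 4.1): "Venipuncture for CBC with Diff, Total and cat hair IgE, cytokines, and gene expression (approximately 50 cc total").
- Visit 3 (section 4.2), for subjects kept for the full monitoring period: "Venipuncture for CBC with diff, cytokines, and gene expression 10 hours post-challenge (approximately 50 cc total").
- Visit 3, for asymptomatic subjects whose FEV1 falls by less than 10%: "subjects will be monitored for 2 hours post challenge and will be discharged following post-challenge venipuncture with rescue medications".
- Visit 4 (section 4.2): "Venipuncture for CBC with Diff, gene expression, cytokines (approximately 50 cc total").

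The procedures table in section 15.1 also marks venipuncture at Visits 1, 3 and 4.

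**The concern.** The two-sample t test and the Mann-Whitney U test both treat the two sets of values as coming from different, unrelated people. Here there is no second group. Each post-challenge value has a partner from the same subject before challenge, and the quantity of interest is the change within that subject.

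An unpaired test leaves the stable differences between subjects in the error term, where a paired test removes them. If a subject's before and after values are positively correlated, the unpaired standard error is too large, the p-value is too large, and an interval built the same way is too wide. Real changes in systemic inflammation or gene expression could be missed. Section 1.1 singles out gene-expression change as a particular interest, and section 5.5 allows up to 50 cc of blood at each draw.

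**Working it through.** **Do the documents supply a paired method elsewhere?** For these endpoints, no. Section 6.4 uses a paired t test, but only to size the later anakinra crossover trials. The Wilcoxon signed-rank test and mixed models are not mentioned.

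**Is there a planned figure to reproduce?** No. The plan gives no sample size, power or effect size for the exploratory comparisons. What follows sizes the consequence under stated assumptions.

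**Inputs from the documents**

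- Significance criterion 0.05 (section 6.3). Sidedness is not stated; two-sided is assumed.
- Screening stops at 25 late-phase responders, with at most 100 subjects screened (section 6.4).

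**Number of subjects with paired blood**

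- Responders only: n = 25. The plan does not state this restriction, and non-responders also give post-challenge blood.
- All challenged, at the late-phase rate of about 50% in section 1.3: 25 / 0.5 = 50.
- All challenged, at the planning rates in section 6.4: 25 / (0.5 × 0.5) = 100.

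**Assumptions not in the documents:** bivariate normal pairs, equal SD before and after, correlation rho from 0.3 to 0.8, true shift 0.4 SD, one unadjusted test.

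**Standard error of the mean change**, with common SD s:

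- Unpaired formula: s × sqrt(2/n).
- Correct for pairs: s × sqrt(2(1 - rho)/n).
- Ratio: 1/sqrt(1 - rho).

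| rho | Ratio |
|---|---|
| 0.3 | 1/sqrt(0.7) = 1.20 |
| 0.5 | 1/sqrt(0.5) = 1.41 |
| 0.7 | 1/sqrt(0.3) = 1.83 |
| 0.8 | 1/sqrt(0.2) = 2.24 |

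The two-sample t quantile has more degrees of freedom, 2n - 2 against n - 1, which offsets this slightly. Across rho 0.3 to 0.8, the expected ratio of interval widths is 1.17 to 2.18 at n = 25 and 1.19 to 2.22 at n = 100.

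**Actual type I error of the unpaired t test (nominal 5%), by simulation:** about 2% at rho 0.3, 0.6% to 0.7% at rho 0.5, and 0.1% or less at rho 0.7. It is about 5% at rho 0.

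**Power for a 0.4 SD shift.** The paired t test has standardised effect 0.4/sqrt(2(1 - rho)), which is 0.34, 0.40 and 0.52 at rho 0.3, 0.5 and 0.7. Paired power agrees with the exact noncentral t calculation within 0.4 percentage points. Each cell shows power as planned versus paired.

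| n | rho 0.3 | rho 0.5 | rho 0.7 |
|---|---|---|---|
| 25 | 25% vs 37% | 21% vs 48% | 16% vs 70% |
| 50 | 51% vs 65% | 51% vs 79% | 52% vs 95% |
| 100 | 84% vs 92% | 89% vs 98% | 94% vs 99.9% |

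The rank tests behave in the same way. At rho 0.7, Mann-Whitney against signed-rank is 16% vs 67% at n = 25 and 92% vs 99.9% at n = 100.

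**A check that does not use the 0.4 SD shift.** Set the effect so that the paired t test has 80% power. At n = 25 the two-sample t test then has 70%, 53% and 25% power at rho 0.3, 0.5 and 0.7. At n = 50 it has 69%, 53% and 23%.

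**The case against.** The best defence is that this is loose wording. The primary endpoint is a within-subject difference, one secondary outcome is a change from baseline, and section 6.4 uses a paired t test, so the authors understand pairing and may mean two time points by two samples. This does not rescue the text. The Mann-Whitney U test is named as the fallback and is an independent-samples test, and section 6.4 shows that the authors write paired when they mean it.

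A second argument concerns the intervals. An interval for a mean change is naturally built from individual differences and would then be correct, which would leave only the p-values wrong. That reading is possible. However, section 6.3 gives no interval method apart from the named tests. At best, the section would report paired intervals beside unpaired p-values that need not agree with them.

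Third, the size of the loss rests on assumed values, including equal variances. If the post-challenge SD were twice the baseline SD, the inflation would be sqrt(5/(5 - 4 × rho)): 1.15, 1.29 and 1.51 at rho 0.3, 0.5 and 0.7. The largest power losses also occur at n = 25, which may not apply. Both points stand as limits on the magnitude, but neither makes the unpaired test appropriate.

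Finally, only exploratory endpoints are involved, and samples keep subject numbers (section 10.2), so the pairing can be restored at analysis. That is true, and it limits the severity.

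**Conclusion.** The concern holds. For the exploratory blood-marker and gene-expression comparisons, section 6.3 prescribes tests that do not fit a single-arm, repeated-sample design. It is also inconsistent with its own promise to report mean changes. This should be fixed.

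With positive within-subject correlation the error is conservative: p-values and unpaired intervals are too large and false positives are not inflated. Negative correlation would reverse this, and at rho 0 nothing is lost. With 50 to 100 subjects and a 0.4 SD shift, the power lost ranges from about 6 percentage points (n = 100, rho 0.7) to about 43 (n = 50, rho 0.7). At n = 25 the loss can be larger.

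These figures depend on the assumed correlation, shift and equal variances. They describe a single test and do not carry over to adjusted inference across the 594-gene panel. The primary endpoint, the secondary IL-1β regressions, the sample size and, with complete pairs, the point estimates of mean change are not affected.

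**What to change.** In section 6.3, replace the two named tests with a paired t test on within-subject change, transformed where skewed, or the Wilcoxon signed-rank test if the differences are not normal. Apply the normality check to the differences. State that the confidence interval is that of the paired mean change.

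Name the time points for each comparison. Visit 1 supplies the pre-challenge sample. The Visit 3 draw is at 10 hours in subjects who stay and around 2 hours in those discharged early, so it is not one common time point. The Visit 4 draw is at 24 hours.

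A mixed model with a subject random effect is an acceptable alternative that uses all three time points and incomplete pairs. It is not identical to the paired tests, and its covariance structure would have to be specified.

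Cost: the paired tests need only a wording change, with no added data or visits. The mixed model needs a short specification. Making the change before analysis also avoids choosing the test after the data are seen.

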The purpose of this study is to identify subjects with mild allergic asthma who experience a LPR after inhalation of *Felis catus* (cat hair) extract. Additionally, in order to better understand the role of IL-1 β in allergen-induced airway inflammation, we will obtain induced sputum to determine if higher baseline sputum IL-1 β concentrations or larger increases in IL-1 β following allergen challenge impact non-specific airway hyperresponsiveness, sputum granulocyte recruitment, sputum mucin content (MUC5AC, MUC5B), markers of systemic inflammation, or changes in expression of inflammatory or allergy-related genes. To this last point, little is known about the mechanisms contributing to response patterns in allergic asthmatics undergoing allergen challenge. We are particularly interested in gene expression changes occurring during the window of time between the EPR and LPR, as these expression changes may dictate whether or not a LPR occurs or to what extent it occurs^{16, 17}.

Once identified, these subjects will be eligible for participation in two randomized, double-blinded, placebo-controlled clinical trials of Anakinra vs placebo administered after allergen challenge for mitigation of features of an asthma exacerbation.

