8 STUDY INTERVENTION ADMINISTRATION

As this is an open-label single arm intervention study, all participants will receive the same treatment without blinding.

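### The exploratory marker and gene-expression analysis compares only before with after challenge, so it cannot show whether changes differ by late phase response

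*Combined protocol and SAP*

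**What the plan says.** Section 6.3 states that "we will use two sample comparison tests to compare systemic inflammatory markers and gene expression levels before and after allergen challenge", and then: "We will use two-sample t tests or Mann Whitney U tests depending on whether the normality assumption is met". Mean changes are to be reported with confidence intervals, and a criterion of p ≤ 0.05 applies throughout. The section names no analysis set for these comparisons and includes no LPR term, subgroup or between-group contrast. None appears elsewhere.

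The listed exploratory endpoint in section 6.2 is that "we will assess the effects of allergen challenge on markers of systemic inflammation and changes in inflammatory gene expression", with a gene panel to "measure differential expression of a panel of 594 immunology-related genes".

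Two other places ask something different. Section 1.1 expresses particular interest in expression changes between the early phase response (EPR) and the LPR, because "these expression changes may dictate whether or not a LPR occurs or to what extent it occurs". Section 5.5 says the blood is drawn partly to find genes involved in how an individual responds to the challenge.

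On design, section 8 states: "As this is an open-label single arm intervention study, all participants will receive the same treatment without blinding". Blood is taken at Visits 1, 3 and 4. For subjects who stay, the Visit 3 draw is listed as "Venipuncture for CBC with diff, cytokines, and gene expression 10 hours post-challenge". Subjects without symptoms whose FEV1 falls by less than 10% are bled and discharged after about 2 hours.

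**The concern.** A before/after test estimates one mean change. It can be significant when LPR and non-LPR subjects change equally, and it can miss a change confined to LPR subjects. It therefore says nothing about whether expression relates to the occurrence or extent of an LPR. The study classifies late response for its primary purpose, yet section 6.3 does not use that variable here.

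The second issue is wording. With one arm and no diluent-only day, the mean change includes anything else that differs between draws. Examples visible in the protocol are time of day (eligibility is checked on the morning of challenge, and the draw is 10 hours post-challenge) and the sputum induction and methacholine procedures that come between the Visit 1 blood and the later draws. Calling the result an effect of allergen claims more than the design supports.

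At stake is the interpretation of an exploratory analysis intended for publication. The primary endpoint, the sample size and the secondary analyses are not affected.

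**Working it through.** **Inputs.** Up to 100 screened, 50% with an EPR and 50% of those with an LPR; screening stops at 25 LPR subjects (section 6.4). 594 genes (section 6.2). Level 0.05 (section 6.3), taken as two-sided. Assumed, because the documents give no values: pre and post values normal with SD 1, correlation 0.5, and the effect sizes below.

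**Plan's own figure.** 100 × 0.5 × 0.5 = 25 LPR subjects, which reproduces section 6.4. That leaves 25 subjects with an EPR only, or 75 without an LPR in all.

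**Who has 10-hour blood.** Section 4.2 ties the 10-hour stay to an FEV1 fall of at least 10%, whereas section 4.8 gives the EPR target as at least 20%. Those who stay are thus not simply the EPR group, and the plan does not give their number. I use 25 vs 25 and 25 vs 75 as illustrative cases. The second counts subjects discharged at 2 hours as non-LPR, relying on the statement in section 1.1 that no LPR occurs without an EPR.

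**Precision of the contrast.** SD of change = √(2 × (1 − 0.5)) = 1. Standard error of the difference in mean change = √(1/n1 + 1/n2).
- 25 vs 25: 0.283, so a 0.8 SD difference is 0.8/0.283 = 2.83 standard errors.
- 25 vs 75: 0.231, so 0.8/0.231 = 3.46 standard errors.

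**Power by simulation for a 0.8 SD rise in LPR subjects only** (Welch test for the contrast):

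| Test, level 0.05 | 25 vs 25 | 25 vs 75 |
|---|---|---|
| Unpaired before/after, as planned | 47% | 20% |
| Paired before/after | 74–75% | 46% |
| Contrast of change by LPR status | 79% | 92% |

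Over correlations 0.3 to 0.7, the contrast at 25 vs 75 has 83% to 99% power.

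**Gene panel.** Bonferroni level = 0.05/594 = 0.000084. Power of the same contrast falls to about 9% (25 vs 25) and 22% (25 vs 75). By the normal approximation, the difference detectable with 80% power at 25 vs 75 rises from 0.65 to 1.10 SD of the change. With no adjustment, a test of nominal size gives 594 × 0.05 = 29.7 false positives under the global null.

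**Regression instead of change scores.** Adjusting for the Visit 1 value gives residual SD √(1 − 0.5²) = 0.87 in place of 1, so the figures above are somewhat low for the regression proposed below.

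**What the contrast cannot do** (25 vs 25):
- Shared drift of 0.2 to 0.5 SD with no allergen effect: significant in 9% to 77% of runs with the planned test and 28% to 93% with a paired test. The contrast stays at 5%.
- Real allergen effect of 0.8 SD shared by both groups: the contrast is again significant in only 5%.
- LPR subjects rise 0.8 SD and the others 0.4 SD: the contrast detects the difference in about 29%, while the paired before/after test is significant in about 98%.

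The contrast therefore removes drift and any common allergen effect alike.

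**The case against.** The strongest reply is that the before/after test fits the endpoint as listed. Sections 2.2 and 6.2 ask about effects of challenge; the LPR sentence is background and appears in no endpoint list. This stands. A reader might infer that the plan fails to analyse its own listed endpoint, and the documents do not support that.

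A reader might also infer that the LPR contrast should replace the before/after estimate because it is immune to drift. It should not: everyone inhales allergen, so the contrast cancels true common effects as well and would leave the listed endpoint without an analysis. The lack of a control can be met here only by restrained wording.

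A third tempting inference is that the contrast would reveal what brings on an LPR. For subjects who stay, the challenge-day draw is at the end of the 3–10 hour window and the next is at 24 hours. Neither shows expression preceding the response.

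Other limits stand too. At 25 vs 25, most of the gain over the planned test comes from pairing (47% to about 75%), not from the contrast (79%). LPR status is bound up with treatment and dose: rescue albuterol depends on FEV1 and distress (sections 1.3 and 9.3), prednisone may be given the next morning for wheeze or reduced FEV1 without a stated order relative to the Visit 4 draw (section 9.4), and cumulative allergen dose varies because the challenge stops at a 20% fall (section 5.1). The drift sizes are assumed. Finally, section 6.3 names no analysis set, so reading the test as covering all subjects is an inference.

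**Conclusion.** The point holds as a gap in an exploratory analysis. The planned comparison suits the listed endpoint but cannot address the between-subject question in sections 1.1 and 5.5, although late response is already being classified. Adding the contrast is worthwhile for moderate to large differences in a few markers: about 79% to 92% power for 0.8 SD at unadjusted 0.05, under assumed normality and correlation 0.5. If screening reached 25 LPR subjects sooner, the comparator would shrink. At the 56% LPR rate of the cat-extract study cited in section 1.4 (about 25 vs 20), the difference detectable with 80% power is 0.84 SD of the change. Across the whole gene panel, power under strict error control is low, so the results would generate hypotheses only. The case for restrained wording rests on the single-arm design and does not depend on the assumed drift.

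**What to change.** In section 6.3:

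1. Keep the before/after estimate as the analysis of the listed endpoint, done as a within-subject comparison, and describe it as change after challenge.
2. Add a prespecified exploratory regression of the log-scale post value on its Visit 1 value and LPR status, with maximum 3–10 hour FEV1 fall as the alternative regressor.
3. Define the sets. For the challenge-day draw, use only subjects who stayed 10 hours. For the 24-hour draw, use all subjects, with those discharged at 2 hours as a separate category; they have no 3–10 hour FEV1 and so cannot enter the model on maximum fall.
4. Apply a false-discovery rule across the 594 genes.
5. Report albuterol or prednisone given before each draw and cumulative allergen dose, with a sensitivity analysis excluding subjects treated before sampling.
6. State the limits: the contrast shows LPR-associated change only, removes effects common to all subjects, is observational, and cannot show expression before the LPR.

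The cost is a paragraph or two of analysis text and some added reporting, with no new visits, samples or subjects.
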